4.2 Secondary Endpoints

1. Incidence of adverse events (serious and device- and/or procedure-related) to 24 hours post-operative.
2. Incidence of adverse events (serious and device- and/or procedure-related) between 24 hours and 28 days post-operative.
3. Technical success defined as successful occlusion of the treated site as seen on post-embolization angiography.
4. Incidence of device observations relating to EmboCube.

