Adverse device effect that has resulted in any of the consequences characteristic of a serious adverse event.

In addition to the ISO14155:2020 definitions, the following study specific definitions apply:

Procedure-Related Adverse Event: an adverse event is considered to be procedure-related when, in the judgment of the Investigator, it is reasonable to believe that the event is associated with the assigned study procedure and is not solely to the device. Other products, surgical techniques, or medications required specifically for the procedure are likely to have contributed to the occurrence of the event.

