7.2 Reportable Adverse Events

For the purpose of this study, events which meet the definition of both serious adverse events and that are potentially device-related and/or procedure-related will be reported.

All deaths will be reported as SAE regardless of Investigator assessment of causality.

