12 STUDY DEFINITIONS

ADVERSE EVENT CAUSALITY

The sponsor and the investigators will use the following definitions to assess the relationship of the serious adverse event to the study device, or the investigation procedure¹.

1. Not related: Relationship to the device, or procedures can be excluded when:

- the event has no temporal relationship with the use of the study device, or the procedures related to application of the study device;
- the serious adverse event does not follow a known response pattern to the medical device (if the response pattern is previously known) and is biologically implausible;
- the discontinuation of medical device application or the reduction of the level of activation/exposure - when clinically feasible - and reintroduction of its use (or increase of the level of activation/exposure), do not impact on the serious adverse event;

¹ Definitions derived from "MDCG 2020-10/1 Safety reporting in clinical investigations of medical devices under the Regulation (EU) 2017/745" May 2020.

- the event involves a body-site or an organ that cannot be affected by the device or procedure;
- the serious adverse event can be attributed to another cause (e.g., an underlying or concurrent illness/ clinical condition, an effect of another device, drug, treatment, or other risk factors);

In order to establish the non-relatedness, not all the criteria listed above might be met at the same time, depending on the type of device/procedures and the serious adverse event.

2. Possible: The relationship with the use of the study device, or the relationship with procedures, is weak but cannot be ruled out completely. Alternative causes are also possible (e.g., an underlying or concurrent illness/ clinical condition or/and an effect of another device, drug, or treatment). Cases where relatedness cannot be assessed, or no information has been obtained should also be classified as possible.

3. Probable: The relationship with the use of the study device, or the relationship with procedures, seems relevant and/or the event cannot be reasonably explained by another cause.

4. Definitely related (Causal relationship): the serious adverse event is associated with the study device, or with procedures beyond reasonable doubt when:

- the event is a known side effect of the product category the device belongs to or of similar devices and procedures;
- the event has a temporal relationship with study device use/application or procedures;

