7.2 SECONDARY OUTCOMES

The secondary outcomes will include the following safety and performance measures:

- Incidence of adverse events (serious and device- and/or procedure-related) to 24 hours post-operative
- Incidence of adverse events (serious and device- and/or procedure-related) between 24 hours and 28 (0/+14) days post-operative

- Technical success defined as successful occlusion of the treated site as seen on post-embolization angiography
- Incidence of device observations related to EmboCube

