8.3 SECONDARY DATA ANALYSES

All secondary endpoints will be tabulated. Means, SDs, and sample size will be used to summarize continuous variables. Distributions of continuous data will be examined and if non-normality is exhibited, medians and interquartile ranges will be presented. Frequencies and percentages will be used to summarize categorical variables. All available data will be used for each endpoint and no imputations will be performed.

Incidence of adverse events to 24 hours post-operative (serious and device- and/or procedure-related)

Endpoint Derivation:

- Serious adverse events as reported by the site, **AND**
- “Seriousness” is checked as anything other than “Not Serious”, **AND**
- Relationship to study device **AND/OR** relationship to study procedure is “Definitely related”

Incidence of adverse events between 24 hours and 28 days post-operative (serious and device- and/or procedure-related)

Endpoint Derivation:

- “Were there any serious and device- or procedure-related adverse events since the 24-hour contact visit?” is checked YES, **AND**
- Serious adverse events as reported by the site and in which “Seriousness” is checked as anything other than “Not Serious”, **AND**
- Relationship to study device **AND/OR** relationship to study procedure is “Definitely related”

Technical success defined as successful occlusion of the treated site as seen on post-embolization angiography

Endpoint Derivation:

- “Was occlusion of the treated area (as seen on post-embolization angiogram) successful?” is checked YES

Incidence of device observations related to EmboCube

Endpoint Derivation:

- “Was procedure aborted due to device observation?” is checked YES

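### SAP 8.3 counts only Definitely related serious events in both secondary adverse-event endpoints, although the endpoints are defined as related with no certainty grade

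*SAP*

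**What the plan says.** The two endpoints are worded alike in both documents. SAP 7.2 gives the first as "Incidence of adverse events (serious and device- and/or procedure-related) to 24 hours post-operative", and Protocol 4.2 gives the second as "Incidence of adverse events (serious and device- and/or procedure-related) between 24 hours and 28 days post-operative". Neither wording limits how certain the relationship must be.

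SAP 8.3 turns each endpoint into a set of conditions joined by AND. In both windows the last condition is that the relationship to the device and/or the "relationship to study procedure is “Definitely related".

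Protocol section 12 grades causality in four steps:

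- **Not related.**
- **Possible.** This is also the default for unclear cases: "Cases where relatedness cannot be assessed, or no information has been obtained should also be classified as possible".
- **Probable.** The relationship "seems relevant and/or the event cannot be reasonably explained by another cause".
- **Definitely related.** The standard is that "the serious adverse event is associated with the study device, or with procedures beyond reasonable doubt when" listed criteria apply.

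Two other provisions bear on what counts as related. Protocol 7.1 calls an event procedure-related when, in the investigator's judgment, "it is reasonable to believe that the event is associated with the assigned study procedure". Protocol 7.2 sets what sites must report: "events which meet the definition of both serious adverse events and that are potentially device-related and/or procedure-related will be reported".

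**The concern.** A derivation should put the endpoint definition into operation. Here it narrows the definition, and neither document announces or justifies the narrowing. Serious events that the investigator thinks possibly or probably caused by the device or procedure are collected, but are then left out of the two endpoints meant to measure them.

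These are secondary, descriptive rates, and no test depends on them. In a mainly descriptive study, though, the reported rate is the result. Protocol 1.5 says the data will feed the product risk analysis, the clinical evaluation report and, if appropriate, the labelling. A rate that can err only in the favourable direction is a poor input to those uses.

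**Working it through.** The plan gives no expected event rate for these endpoints, so there is no figure to reproduce. The check sets the provisions side by side and then illustrates the size.

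**Which grades count under each provision**

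| Provision | Possible | Probable | Definite |
|---|---|---|---|
| Protocol 4.2, SAP 7.2 (endpoint definitions) | no grade excluded | no grade excluded | counted |
| Protocol 7.1 (procedure-related event) | arguable | fits | fits |
| Protocol 7.2 (reportable events) | reported | reported | reported |
| SAP 8.2 (primary safety, to 24 h) | no grade filter | no grade filter | no grade filter |
| SAP 8.4 (safety summary) | no cut-off stated | no cut-off stated | counted |
| SAP 8.3 (both secondary endpoints) | **not counted** | **not counted** | counted |

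Three consequences follow.

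1. A Probable event meets the Protocol 7.1 standard for a procedure-related event, yet SAP 8.3 does not count it.
2. Protocol section 12 assigns unassessable events to Possible as a cautious default. SAP 8.3 reverses the effect, because that grade removes the event from the endpoint.
3. Take a serious event at 12 hours that is graded Probable and entered by the site as related. It fails the primary safety derivation in SAP 8.2 but is missing from the 24-hour incidence in SAP 8.3. In the later window, the site's YES to the related-event question is overridden unless the grade is Definite.

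**Direction.** Let x be the number of subjects with at least one serious event graded Possible or higher for device or procedure, and d the number with at least one graded Definite. Since d ≤ x, the reported rate d/N cannot exceed the defined rate x/N. The shortfall is (x − d)/N.

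**Size, by illustration.** N = 100 is the planned minimum (SAP 5.5). The values of x and d are assumptions. The intervals are Clopper-Pearson 95%, the method named in SAP 8.1: for k events the lower limit is the 0.025 quantile of Beta(k, N − k + 1) and the upper limit is the 0.975 quantile of Beta(k + 1, N − k). For k = 0 the lower limit is 0 and the upper is 1 − 0.025^(1/100) = 3.6%.

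| x (Possible or higher) | Rate as defined | d (Definite) | Rate under SAP 8.3 | Shortfall, points |
|---|---|---|---|---|
| 6 | 6.0% (2.2–12.6) | 0 | 0.0% (0–3.6) | 6 |
| 6 | 6.0% (2.2–12.6) | 3 | 3.0% (0.6–8.5) | 3 |
| 6 | 6.0% (2.2–12.6) | 6 | 6.0% (2.2–12.6) | 0 |
| 10 | 10.0% (4.9–17.6) | 1 | 1.0% (0.03–5.4) | 9 |
| 10 | 10.0% (4.9–17.6) | 4 | 4.0% (1.1–9.9) | 6 |
| 10 | 10.0% (4.9–17.6) | 5 | 5.0% (1.6–11.3) | 5 |
| 10 | 10.0% (4.9–17.6) | 10 | 10.0% (4.9–17.6) | 0 |

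With x = 10 and d = 4 or fewer, the printed interval lies wholly below 10%. This is not a test, because d is a subset of x in the same subjects. It shows only that the interval a reader sees need not cover the rate for the endpoint as defined.

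**The case against.** The strongest reply is that the events are not lost. The complement of the primary safety result in SAP 8.2 is, as drafted, an unfiltered subject-level incidence of related serious events to 24 hours, and it is tabulated for ITT and PP. SAP 8.4 tabulates subjects with a related serious event and lists each event with its start date and relationship. SAP 8.3 also states its filter openly. All of this is true and limits the harm.

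It does not remove the problem. The figure from SAP 8.2 covers only the first 24 hours and comes from a derivation that itself departs from the primary endpoint of unanticipated serious device effects, so it may not survive correction. SAP 8.4 is cumulative, with no split at 24 hours and no stated cut-off for related. No planned table gives an unfiltered rate from 24 hours to 28 days, and the two named endpoint rows stay filtered.

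A second reply is that Possible should not be in the headline count. Section 12 describes that grade as a weak link that cannot be excluded, Protocol 7.1 speaks only to procedure-related events, and Protocol 7.2 is a reporting rule rather than an endpoint definition. This has some force: the case for Probable is clear from the definitions, while counting Possible is a conservative choice. It affects which wider cut-off to adopt and does not support Definite only.

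**Conclusion.** The concern holds. SAP 8.3 as written does not measure the endpoints that Protocol 4.2 and SAP 7.2 define, and its error can go only towards a lower reported incidence. Confidence is high, because this rests on the text and on no assumed figure.

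The size is unknown. It depends on how many related serious events occur and how they are graded, and the documents give neither. In the illustrations it runs from no effect, when every event is graded Definite, to 9 percentage points. The results affected are secondary and descriptive; sample size and the clinical success result are untouched. It should be corrected before the analysis is run.

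**What to change.** - **SAP 8.3, both derivations:** replace the Definitely related condition with Possible, Probable or Definitely related, for device and/or procedure. Show counts by grade as sub-rows, including Definite only, so that readers can see what including Possible adds.
- **SAP 8.4:** state the same cut-off for related, so that the safety summary and the endpoint rows agree.
- **If the sponsor wants a narrower count:** write the restriction into the endpoint definition and give the reason there.

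The cost is a few lines of SAP text and slightly longer tables. Relationship to device and procedure is already recorded for every reportable event (Protocol 7.4.1), so no new data are needed. The reported rates may look less favourable, and including Possible will count some events that were not truly related, which is why the sub-rows matter.

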5.4 Withdrawal

Subjects may withdraw at any time from the study without prejudice; participation is entirely voluntary. If a subject prematurely terminates from the study, the reason for termination will be recorded in the eCRF.

The Investigator should follow all unresolved serious adverse events until the events are resolved, the subject is lost to follow-up, the subject has withdrawn consent, the subject completes the study follow-up, or the adverse event is otherwise explained.

All reasonable efforts will be made to obtain complete data for all subjects; however, missing observations will occur due to loss to follow-up, withdrawal, or variation in site standard of care assessments.

Sites shall make all reasonable efforts to contact subjects who do not attend for a routine clinic visit between 4 to 6 weeks by telephone to confirm status. In the event subject does not respond to a final contact attempt via certified letter, subject will be documented as lost to follow-up on the Study Exit form. Subjects who withdraw consent after treatment will have their data evaluated until the time of their withdrawal (unless consent for data retention is removed in accordance with local or national regulations). Subjects who withdraw or are lost to follow-up will not be replaced.

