7.4.2 Reporting Requirements for Serious Adverse Events

All serious and potentially device and/or procedure-related adverse events, and all deaths must be reported to the Sponsor within 24 hours of knowledge of the event or by the end of the next working day. This may be done via eCRF or by phone, fax, or email using the contact details provided separately to sites.

The Sponsor will review all reported events for potential reporting in accordance the requirements of Regulation (EU)2017/745 of the European Parliament and of the Council of 5 April 2017 on Medical Devices (MDR), and any applicable guidance(s). Sponsor may request medical record documentation (e.g., procedure notes, operative notes, discharge summary, relevant progress notes, imaging, or lab studies) to facilitate this review.

The Sponsor will determine whether all of the local Investigators need to be informed immediately of an SAE, or whether this can be postponed until the next regularly scheduled study update.

The Sponsor will ensure reporting of applicable events to Regulatory Authorities as clinical study safety reports, if required by Local/national regulations.

The Investigator is responsible for reporting applicable serious adverse events to their EC/IRB as required by EC/IRB procedures and local/national regulations. A copy of each EC/IRB safety report will be provided to Sponsor.

Local, specific safety reporting will be specified in a separate safety plan.

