8 STATISTICAL METHODOLOGY

8.1 GENERAL METHODOLOGY

Final analyses will be performed after all study subjects have completed the final follow-up visit, defined according to the protocol as 28 (0/+14) days.

For continuous variables, outputs will be presented with mean, standard deviation (SD), median, minimum, and maximum values. Mean and median values will be rounded to a single decimal place while SD will be rounded to two decimal places. When appropriate, a corresponding 95% confidence interval (CI) will be calculated. Categorical variables (e.g., sex, race) will be reported using frequencies and percentages. All percentages will be rounded to one decimal place. If percentages do not add up to 100% due to rounding, a footnote explanation will be provided accordingly.

When the mean is not an appropriate measure of central tendency, alternative statistics will be considered (e.g., median). When the distribution of a variable does not support the use of parametric statistics, nonparametric approaches or data transformations may be implemented. If data transformations are used, they will be specified in the final clinical report.

Correlation analyses will be used to analyze relationships for continuous variables. Independent t-tests will be conducted to test differences for continuous variables between binary groups. A Fisher's exact test will be used to analyze the relationships between categorical variables. P-values less than or equal to 0.05 will be considered significant. All p-values will be rounded to 3 decimal places and will be presented as "<0.001" if less than 0.0005.

Time-dependent response variables will be expressed using the Kaplan-Meier curve, and the hazard ratio and the 95% CI will be reported.

Data for all categorical endpoints are shown with the number of patients, percentage, and Clopper-Pearson's exact 95% CI.

Descriptive statistics will be used to examine demographic and baseline characteristics and to perform other efficacy analyses.

Each table generated will have headers that include the total sample size (N). Frequencies and percentages for categorical variables will be calculated using the number of subjects (n) with non-missing values.

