8.1.3 HANDLING OF MISSING DATA

No imputation of missing data is planned.

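### The 24-hour-to-28-day adverse-event endpoint depends on a follow-up question being ticked YES, with no rule for a blank answer, so a related serious event already on the AE form can go uncounted

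*SAP*

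**What the plan says.** SAP 8.3 lists three conditions for the late-window endpoint, all of which must hold:

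- The follow-up question: "Were there any serious and device- or procedure-related adverse events since the 24-hour contact visit?” is checked YES, AND".
- The record itself: "Serious adverse events as reported by the site and in which “Seriousness” is checked as anything other than “Not Serious".
- Causality, to the device and/or the procedure; for the procedure the wording is "relationship to study procedure is “Definitely related".

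The 24-hour endpoint in the same section uses only the seriousness and causality conditions on site-reported records. It has no question that must first be answered YES.

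On missing answers, SAP 8.1.3 says "No imputation of missing data is planned", and SAP 8.1 says "Frequencies and percentages for categorical variables will be calculated using the number of subjects (n) with non-missing values". SAP 8.3 also commits to using whatever data are available for each endpoint.

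On early leavers, Protocol 5.4 says "Subjects who withdraw consent after treatment will have their data evaluated until the time of their withdrawal", subject to local rules on data retention; subjects who are lost are recorded on the Study Exit form. On the flow of events, Protocol 7.4.2 says "All serious and potentially device and/or procedure-related adverse events, and all deaths must be reported to the Sponsor within 24 hours of knowledge", or by the end of the next working day. Protocol 7.4.1 has reportable events entered on the eCRF through day 28. In Table 1 of both documents, the only data-collection column after 24 hours is the follow-up at 28 to 42 days.

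**The concern.** The event record and the follow-up question reach the database by different routes. The record is entered when the site learns of the event. The question asks about the period after the 24-hour contact, which fits a form completed at the 28-to-42-day follow-up. A subject can therefore have a serious, definitely related event on the AE form from day 3 and no answer to the question, because that subject died, withdrew or was lost before the follow-up. Read literally, the derivation rejects that record.

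Blank answers would not fall at random. They would come from subjects who left early, and a fatal related event is itself a reason for leaving early. What is at stake is the late-window rate in a named secondary safety endpoint. Protocol 1.5 says the study data are to feed the product risk analysis and may lead to updates of the clinical evaluation report and labeling.

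**Working it through.** **The plan's own figures.** No rate or precision target is stated for this endpoint. The 100 subjects and the 15% loss belong to 24-hour clinical success. With one-sided alpha 0.05 and variance at 0.90, n = 0.90 × 0.10 × (1.645 + 0.842)² / (0.90 − 0.82)² = 86.9, so 87. Then 87/0.85 gives 103, and 87 × 1.15 gives 101, both close to the stated 100. The point below does not affect that calculation. The 15% is borrowed only as a convenient size for the group with a blank answer.

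**Logic check.** Take an AE record that is serious and definitely related, with onset after 24 hours.

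- Question YES: all three conditions hold and the event is counted.
- Question NO: the first condition fails and the event is not counted, although the record contradicts the answer.
- Question blank: the first condition is not met and the event is not counted. If the derived value is treated as missing, SAP 8.1 removes the subject from the denominator. If it is treated as not YES, the subject stays in as a non-event. The SAP does not say which.

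In the 24-hour endpoint there is no such question to fail, so the two windows use different rules.

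**Direction.** Let N be the subjects, m those with a blank answer, e the subjects with a qualifying late event, and k the number of those e whose answer is blank.

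- Without the question: e/N.
- As written, blanks excluded: (e − k)/(N − m).
- As written, blanks kept as non-events: (e − k)/N.

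The second is below the first when k/e > m/N, that is, when blank-answer subjects hold more than their share of events. It is above when they hold less. The third can never exceed the first.

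**Illustrations.** All assume N = 100 under follow-up at 24 hours and m = 15. The event counts are assumptions. With e = 5, the rate without the question is 5/100 = 5.0% (Clopper-Pearson 95% CI 1.6 to 11.3), and as written:

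| k | blanks excluded | blanks kept |
|---|---|---|
| 0 | 5/85 = 5.9% | 5/100 = 5.0% |
| 1 | 4/85 = 4.7% | 4/100 = 4.0% |
| 2 | 3/85 = 3.5% | 3/100 = 3.0% |
| 3 | 2/85 = 2.4% | 2/100 = 2.0% |

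With e = 7 and k = 3: 4/85 = 4.7% (1.3 to 11.6) against 7/100 = 7.0% (2.9 to 13.9). This assumes an event proportion of 3/15 = 20% in early leavers against 4/85 = 4.7% in the rest.

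With e = 3 and k = 3: 0/85 (0 to 4.2) against 3/100 = 3.0% (0.6 to 8.5).

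**The case against.** The strongest reply is that the mechanism is partly inferred. The eCRF is not among the documents, so it is not established that the question can be answered only at a live contact. Protocol 6.4 has follow-up data collected by reviewing the available medical records to day 28, with the telephone call as a fallback. Protocol 11.2 treats chart review as one trigger for completing the eCRF. A site could therefore answer YES for a subject who died on day 4. Protocol 10.8 provides for remote review and queries, and SAP 8.1.1 for cleaning; a related serious record beside a blank or NO answer is an obvious query. This stands, and it would reduce the loss. It does not remove the point: nothing requires the question to be completed when a subject exits, and no rule says what to do if it is not.

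A reader might also infer that such events vanish from the report. They do not. SAP 8.4 summarises the collected related events over the whole follow-up without the question, and the AE listing shows each one. That confines the effect to this endpoint row in the ITT and PP tables. It does not repair the row, since 8.4 is cumulative and gives no rate for the late window, and the row could disagree with it.

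Finally, the 15% is a sample-size allowance, not a forecast of blank forms, and the event splits above have no source in the documents. That is correct, and they are offered only as illustration. The restriction to definite relatedness is a separate matter and applies whatever the answer to the question.

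**Conclusion.** The point holds as a gap in the derivation. As written, SAP 8.3 can discard a qualifying event that is already recorded. That is inconsistent with Protocol 5.4 for withdrawn subjects and with the SAP's own commitment to use available data. It arises only if the question is left blank (or answered NO against the record).

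Two stronger readings are not supported. One is that a subject who dies of a related event before day 28 can never be counted; record review may supply the answer. The other is that the rate is always biased downward; with no events among the blanks and the blanks excluded, it rises from 5.0% to 5.9% in the illustration. The size cannot be derived from the documents.

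The endpoint is descriptive and secondary, with no threshold or stopping rule attached, and the primary endpoints and sample size are untouched. This should be fixed before the analysis, but it does not threaten the study's main conclusions.

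**What to change.** In SAP 8.3, remove the follow-up question from the late-window derivation. Count AE-form records by onset after 24 hours and by day 28, seriousness and relationship, whatever the subject's exit status. Use as denominator the ITT subjects still under follow-up at 24 hours. Beside the rate, report how many exited before day 28, by reason (death, withdrawal, lost); SAP 7.4 already tabulates non-completers and their reasons. Keep the question as a data-cleaning cross-check, with a query raised whenever it disagrees with the AE form or is blank.

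The onset limits need to be written out. SAP 7.2 ends the window at 28 (0/+14) days while SAP 8.3 and the protocol say 28. SAP 8.4 lists a start date but no time, so an event dated the day after the procedure needs an allocation rule.

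The cost is SAP wording and programming; AE start dates and exit reasons are already collected. The downside is that the reported late event rate may rise slightly.
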